2.4.4.1.8 Subgroup analyses

To assess the homogeneity of the treatment effect across various subgroups, treatment-by-subgroup factor and time point-by-subgroup factor interaction terms and a subgroup factor term will be added in the primary MMRM model. Within each subgroup, baseline adjusted LSmeans estimates at Week 24 will be provided for both treatment groups with their corresponding SEs and 95% CIs, as well as their difference with the corresponding 95% and 90% CIs. Subgroups of interest are:

- Randomization stratum (as per IRT).
- Gender (male/female).
- Both Background therapy (yes/no) definitions defined in [Section 2.4.2](#).
- Disease duration of non-Raynaud's phenomenon (<20 months vs \geq 20 months).
- Auto antibodies (Centromere Antibodies, RNA Polymerase III Antibody, Scl-70 Antibody, [if size allows] and ANA staining pattern [Centromere vs. Non-Centromere staining pattern]).
- Geographical region (Estonia, Romania, Russia, Poland and Ukraine vs Rest of the World).

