1 OVERVIEW AND INVESTIGATIONAL PLAN

1.1 STUDY DESIGN AND RANDOMIZATION

This study will be a multinational, randomized, double blind, placebo controlled, 2 parallel groups, proof of concept Phase 2 study to assess the efficacy and safety of SAR156597 200 mg administered subcutaneously once a week over a 24 week period to patients with diffuse Systemic Sclerosis (SSc).

After a screening phase of up to 4 weeks, patients will be centrally randomized (using allocation from block randomization schedule with stratifying factors) via Interactive Response Technology (IRT) in a 1:1 ratio to 1 of the 2 treatment groups and treated double-blind for approximately 6 months.

Randomization will be stratified based upon the patients' medical history of SSc ILD (yes or no).

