2 STATISTICAL AND ANALYTICAL PROCEDURES

2.1 ANALYSIS ENDPOINTS

2.1.1 Demographic and baseline characteristics

The baseline value is defined as the last available value before the first administration of the Investigation Medicinal Product (IMP).

All baseline safety and efficacy parameters are presented along with the on-treatment summary statistics in the safety and efficacy sections ([Section 2.4.4](#) and [Section 2.4.5](#)).

Demographic characteristics

Demographic variables are gender (Male, Female), ethnicity (Hispanic or Latino, Not Hispanic or Latino, Not reported, Unknown), race (American Indian or Alaska Native, Asian, Black or African American, Native Hawaiian or other Pacific Islander, White, Not reported, Unknown), age in years (quantitative and qualitative variable: <45, [45-65[, [65-75[and ≥ 75 years) and Body Mass Index (BMI) in kg/m² (quantitative variable and qualitative variable: <30 and ≥ 30).

Medical or surgical history

Medical (or surgical) history includes previous relevant medical and surgery history collected at baseline.

This information will be coded using the version of Medical Dictionary for Regulatory Activities (MedDRA) currently in effect at Sanofi at the time of database lock.

Disease characteristics at baseline

Specific disease history includes disease duration from the time of first non-Raynaud's phenomenon manifestation (months), any systemic sclerosis history and mRSS at baseline. The auto-antibodies specific to systemic sclerosis (centromere antibodies, RNA polymerase III antibody, Scl-70 antibody and ANA staining pattern) and stratification factor (with/without medical history of SSc-ILD) as per IRT and as per electronic case report form (e-CRF) will be also presented.

Alcohol habits at baseline

Alcohol habits (frequency of alcoholic drinks in the last 12 months (Never/At least monthly/At least weekly/At least daily/Occasionally), number of standard drinks (1 or 2/Greater than 2 where standard drink means 1 pint/bottle of beer, 1 glass of wine, 1 shot of hard liquor...) per day when drinking alcohol.

Other baseline characteristics

Other baseline characteristics include weight in kilograms (quantitative variable and qualitative variable: <50, [50-100[, ≥100).

Any technical details related to computation, dates, and imputations for missing dates are described in [Section 2.5](#).

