2.2.1 Randomization and drug dispensing irregularities

Randomization and drug-dispensing irregularities occur whenever:

1. A randomization is not in accordance with the protocol-defined randomization method, such as
 - a) An ineligible patient is randomized,
 - b) A patient is randomized based on an incorrect stratum, or
 - c) A patient is randomized twice.

OR
2. A patient is dispensed an IMP kit not allocated by the protocol-defined randomization, such as
 - a) A patient at any time in the study is dispensed a different treatment kit than as randomized (which may or may not contain the correct-as-randomized IMP), or
 - b) A non-randomized patient is treated with IMP reserved for randomized patients.

Randomization and drug-dispensing irregularities will be monitored throughout the study and reviewed on an ongoing basis.

All randomization and drug-dispensing irregularities will be documented in the clinical study report. If the number of irregularities is large enough to make a tabular summary useful, the irregularities will be categorized and summarized among randomized patients (number and percentages). Non-randomized, treated patients will be described separately.

Randomization and drug-dispensing irregularities to be prospectively identified include but are not limited to:

Randomization and drug allocation irregularities

Kit dispensation without IRT transaction

Erroneous kit dispensation (IMP number actually administered to the subject is different from the IMP number allocated by IRT)

Kit not available

Stratification error (Wrong stratum of randomization)

Patient switched to another site

Randomization of a non-existent subject

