2.4.4.1.4 Sensitivity to error in randomization strata

In order to assess the robustness of the primary analysis to randomization stratum mistakes (ie, the stratum recorded in IRT differs from the actual one), if more than 15% of patients have been randomized to the wrong stratum, the MMRM model will be re-run including the actual stratum as per the eCRF instead of the stratum recorded in IRT.

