2.4.4.2 Analyses of secondary efficacy endpoints

All secondary endpoints are described in [Section 2.1.3.2](#) and will be analyzed using the ITT population.

Change in continuous secondary efficacy endpoints (HAQ-DI composite score, observed FVC, observed DLco [corrected for hemoglobin]) from baseline to Week 24 will be analyzed using the same MMRM model as for the primary endpoint. Specifically, the model will contain fixed categorical effects of treatment group (placebo, SAR156597), randomization strata (as per IRT, SSc-ILD: Yes/No), time point (Week 4 [only for HAQ-DI], Week 8 [only for HAQ-DI], Week 12 and Week 24), randomization strata-by-time point interaction and treatment-by-time point interaction, as well as the continuous fixed covariates of corresponding baseline value and baseline-by-time point interaction. All post-baseline data available from Week 4 for HAQ-DI, Week 12 for FVC and DLco, to Week 24 analysis windows will be included in the analysis, regardless of adherence to treatment. Missing data will be accounted for by the MMRM. The studentized residuals of the MMRM will be analyzed as for the primary endpoint.

This model will provide baseline adjusted LSmeans estimates at Week 24 for both treatment groups with their corresponding standard errors (SEs) and 95% CIs. The SAR156597 to placebo difference of these estimates will be provided with its corresponding 95% and 90% CIs and p-value.

Within each randomization stratum (as per IRT, SSc-ILD: Yes/No), baseline adjusted LSmeans estimates at Week 24 will also be provided for both treatment groups with their corresponding SEs and 95% CIs, as well as their difference with the corresponding 95% and 90% CIs.

In order to assess the robustness of the analyses to randomization stratum mistakes (ie, the stratum recorded in IRT differs from the actual one), if more than 15% of patients have been randomized to the wrong stratum, the MMRM model will be re-run including the actual stratum as per the eCRF instead of the stratum recorded in IRT.

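### SSc-ILD subgroup estimates are split by the IRT stratum only; splitting by the actual e-CRF history costs almost nothing and avoids a possible dilution (minor)

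*SAP*

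**What the plan says.** Allocation is stratified on one factor (SAP 1.1): "Randomization will be stratified based upon the patients' medical history of SSc ILD (yes or no". The main MMRMs adjust for that factor as recorded in IRT.

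The same IRT entry defines the ILD-specific results:

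- SAP 2.4.4.1.8, whose purpose is to check whether the mRSS effect is homogeneous, lists as a subgroup "Randomization stratum (as per IRT".
- SAP 2.4.4.2, for HAQ-DI, observed FVC and observed DLco: "Within each randomization stratum (as per IRT, SSc-ILD: Yes/No), baseline adjusted LSmeans estimates at Week 24 will also be provided for both treatment groups".
- The subgroup column of SAP Appendix B repeats the IRT stratum for all four endpoints, with no condition attached.

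The SAP also expects that some entries may be wrong, and it holds the corrected value:

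- SAP 2.2.1 lists among the irregularities to be identified prospectively "Stratification error (Wrong stratum of randomization".
- SAP 2.1.1 presents both versions at baseline: "stratification factor (with/without medical history of SSc-ILD) as per IRT and as per electronic case report form (e-CRF) will be also presented".
- SAP 2.4.4.1.4 (primary endpoint) provides that "if more than 15% of patients have been randomized to the wrong stratum, the MMRM model will be re-run including the actual stratum". SAP 2.4.4.2 has the same rule for the secondary endpoints: "the MMRM model will be re-run including the actual stratum as per the eCRF instead of the stratum recorded in IRT".

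**The concern.** The IRT stratum is the right covariate for the main comparison, because allocation was balanced on it. A subgroup estimate answers another question: how large the effect is in patients with, and in patients without, a history of ILD. For that, a patient entered under the wrong stratum carries the wrong label. Gender, background therapy, disease duration and autoantibodies in 2.4.4.1.8 are all taken from the patient's own characteristics; ILD history is taken from the randomization call.

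If errors occur, each IRT group mixes the two ILD groups and the two estimated effects move towards each other. That is a bias towards homogeneity, the property the section is meant to assess. It matters most to a reader of the FVC and DLco results, where ILD history is the natural candidate for an effect modifier.

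**Working it through.** **Inputs.** From SAP 1.3: 94 patients, 47 per arm, difference 3.6, SD 7, one-sided alpha 5%. From SAP 2.4.4.1.4 and 2.4.4.2: the 15% trigger. Assumed, because the documents do not give them: the number of stratum errors, the ILD split, and any true difference in effect by ILD history.

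**The plan's own figure.** SE = 7 × √(2/47) = 1.444; 3.6/1.444 − 1.645 = 0.848; power = Φ(0.848) = 80.2%, against the stated 80%. No calculation is given for subgroups.

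**Trigger.** 15% of 94 = 14.1. Fourteen errors (14.9%) trigger nothing; the re-run starts at 15.

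**Dilution.** The stratum is fixed before allocation, so errors are taken as independent of arm. Let PPV and NPV be the shares correctly labelled in the IRT-yes and IRT-no groups. Then

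expected IRT-based difference = true difference × (PPV + NPV − 1).

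With 47 true ILD patients and errors split evenly:

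- 5 errors: 2 × (44.5/47) − 1 = 0.89
- 10 errors: 2 × (42/47) − 1 = 0.79
- 14 errors: 2 × (40/47) − 1 = 0.70

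At 14 errors, for other splits and directions:

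| True ILD patients | All ILD entered as no ILD | All no ILD entered as ILD | Evenly split |
|---|---|---|---|
| 30 | 16/16 + 64/78 − 1 = 0.82 | 30/44 + 50/50 − 1 = 0.68 | 23/30 + 57/64 − 1 = 0.66 |
| 47 | 33/33 + 47/61 − 1 = 0.77 | 47/61 + 33/33 − 1 = 0.77 | 40/47 + 40/47 − 1 = 0.70 |
| 60 | 46/46 + 34/48 − 1 = 0.71 | 60/74 + 20/20 − 1 = 0.81 | 53/60 + 27/34 − 1 = 0.68 |

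The range is 66% to 82%. An uneven mix lowers it only marginally: with 30 true ILD patients, 5 errors one way and 9 the other give 25/34 + 55/60 − 1 = 0.65.

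**Size against noise.** Suppose the true mRSS effects were 5.4 with ILD and 1.8 without, a difference of 3.6. With 14 evenly split errors the IRT groups give 0.851 × 5.4 + 0.149 × 1.8 = 4.86 and 0.851 × 1.8 + 0.149 × 5.4 = 2.34, a difference of 2.53. The loss is 1.07 points. In 20,000 simulated trials the mean difference was 2.53 by IRT and 3.60 by actual stratum. With equal strata there are 94/4 = 23.5 patients per arm and stratum, so the SE of this contrast is 7 × √(4/23.5) = 2.89 and its 95% half-width is 1.96 × 2.89 = 5.66.

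**Does the 15% rule repair the split?** For mRSS, no. The re-run MMRM swaps one covariate for another and has no treatment-by-stratum term, so it gives no ILD-specific effect. For the secondary endpoints, the rule follows directly after the within-stratum paragraph and speaks of the analyses in general, so above 15% it may be meant to cover those estimates. Appendix B places the re-run under supportive analysis and leaves the subgroup column as IRT.

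**Fitting both versions.** Section 2.4.4.1.8 adds a subgroup term and its time interaction to a model that already holds the IRT stratum and its time interaction. An e-CRF subgroup term added beside these is nearly aliased with them when few patients differ, and fully aliased when none do. In a one-time-point analogue (94 patients, equal strata, SD 7, equal-weight LSmeans), 2 discordant patients raise the SE of a per-arm subgroup LSmean from 1.46 to 2.92. The SE of the treatment difference hardly changes (2.04 to 2.05).

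**The case against.** The strongest reply is that the dilution needs two things the documents do not show: stratum errors, and a true difference in effect by ILD history. Without either, nothing is lost. That stands. A reader might infer that patients are known to sit in the wrong group and that a real ILD difference is being hidden; the SAP only provides for errors and reports none. Fourteen errors is also the ceiling below the trigger, not an expected number.

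Second, comparisons within IRT strata remain valid randomized comparisons on a factor fixed before allocation. This stands too, and there is no case against the IRT stratum as covariate in the main models. It does not make the IRT entry the better label for ILD history.

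Third, the e-CRF value is recorded medical history. The protocol flow chart schedules no HRCT, so an e-CRF split is not a split by verified ILD. Full recovery of a true difference is therefore an assumption, although the SAP itself treats the e-CRF value as the actual stratum.

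Fourth, this is a proof-of-concept trial, the secondary and exploratory p-values are descriptive, no decision rests on the subgroups, and discordance will be visible because both strata are tabulated. This limits the severity. It does not supply the ILD-specific estimates by actual history.

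**Conclusion.** The point holds as a minor, nearly free improvement. As written, the SAP yields no ILD-specific mRSS effect by actual history at any error rate, and none for HAQ-DI, observed FVC or observed DLco at or below 15% errors. Above 15%, the text for the secondary endpoints is open to either reading, so it would go too far to say that the actual stratum is never used there.

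Conditional on errors and on a true ILD difference, about 89% of that difference is kept at 5 errors and 70% at 14 (equal strata, even errors), or 66% to 82% at 14 over 30 to 60 true ILD patients with one-way or even errors. In the assumed mRSS example the loss of about 1.1 points is well inside the 5.7-point half-width, so a trial of this size could hardly establish such a difference under either label. The primary test and the main secondary comparisons are unaffected.

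**What to change.** - In 2.4.4.1.8, in the within-stratum paragraph of 2.4.4.2 and in the subgroup column of Appendix B, define the SSc-ILD subgroup by the e-CRF (actual) history, at any error rate.
- In that ILD subgroup model only, replace the IRT stratum and its time interaction by the e-CRF stratum and its time interaction. Do not fit both.
- Keep the IRT stratum as covariate in the primary MMRM and the main secondary MMRMs.
- If any patient differs between the two sources, show the IRT-based split as a supportive table.

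The cost is an edit in three places, one sentence of model specification and possibly one extra table. Both variables are already collected and tabulated, and the primary test does not change. The edit should be made before unblinding, so that the choice of label cannot depend on the results.

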2.4.4.2 Analyses of secondary efficacy endpoints

All secondary endpoints are described in [Section 2.1.3.2](#) and will be analyzed using the ITT population.

Change in continuous secondary efficacy endpoints (HAQ-DI composite score, observed FVC, observed DLco [corrected for hemoglobin]) from baseline to Week 24 will be analyzed using the same MMRM model as for the primary endpoint. Specifically, the model will contain fixed categorical effects of treatment group (placebo, SAR156597), randomization strata (as per IRT, SSc-ILD: Yes/No), time point (Week 4 [only for HAQ-DI], Week 8 [only for HAQ-DI], Week 12 and Week 24), randomization strata-by-time point interaction and treatment-by-time point interaction, as well as the continuous fixed covariates of corresponding baseline value and baseline-by-time point interaction. All post-baseline data available from Week 4 for HAQ-DI, Week 12 for FVC and DLco, to Week 24 analysis windows will be included in the analysis, regardless of adherence to treatment. Missing data will be accounted for by the MMRM. The studentized residuals of the MMRM will be analyzed as for the primary endpoint.

This model will provide baseline adjusted LSmeans estimates at Week 24 for both treatment groups with their corresponding standard errors (SEs) and 95% CIs. The SAR156597 to placebo difference of these estimates will be provided with its corresponding 95% and 90% CIs and p-value.

Within each randomization stratum (as per IRT, SSc-ILD: Yes/No), baseline adjusted LSmeans estimates at Week 24 will also be provided for both treatment groups with their corresponding SEs and 95% CIs, as well as their difference with the corresponding 95% and 90% CIs.

In order to assess the robustness of the analyses to randomization stratum mistakes (ie, the stratum recorded in IRT differs from the actual one), if more than 15% of patients have been randomized to the wrong stratum, the MMRM model will be re-run including the actual stratum as per the eCRF instead of the stratum recorded in IRT.

In addition, the observed FVC at Week 24 will also be analyzed through a linear mixed effects model. The model will assume random intercept and random slope to take into account between-subject heterogeneity and assume a linear evolution of the observed FVC over time (time will be included as a continuous variable in the model). The analysis will be also adjusted for fixed categorical effects of treatment group (placebo, SAR156597), randomization strata (as per IRT, SSc-ILD: Yes/No). The following interaction terms will be added to the model: treatment-by-time and randomization strata-by-time. All the visits are taken into account in this analysis.

2.4.4.3 Multiplicity issues

No adjustment will be made. For secondary and exploratory efficacy endpoints, p-values will be provided for descriptive purpose only.

2.4.4.4 Analyses of exploratory efficacy endpoints

All exploratory endpoints are described in [Section 2.1.4](#) and will be analyzed using the ITT population unless otherwise specified.

Change in continuous exploratory efficacy endpoints from baseline to Week 24 will be analyzed using the same MMRM model as for the primary and continuous secondary efficacy endpoints. Specifically, the model will contain fixed categorical effects of treatment group, randomization strata (as per IRT), time point, randomization strata-by-time point interaction and treatment-by-time point interaction, as well as the continuous fixed covariates of corresponding baseline value and baseline-by-time point interaction. All post-baseline data available from Week 4 to Week 24 analysis windows will be included in the analysis, regardless of adherence to treatment. Missing data will be accounted for by the MMRM. This model will provide baseline adjusted LSmeans estimated at Week 24 in both treatment groups with their corresponding 95% CIs. The SAR156597 to placebo differences of these estimates will be provided with its corresponding 95% and 90% CIs and p-value.

Change in continuous exploratory efficacy endpoints from baseline to Week 35 will be analyzed using the same model. All post-baseline data available from Week 4 to Week 35 analysis windows will be included in the analysis, regardless of adherence to treatment.

2.4.4.4.1 mRSS

Responder rates (proportion of patients with an improvement from baseline in mRSS of at least 20%, 40% and 60%) at Week 24 and Week 35 will be analyzed using a logistic regression with the categorical effects of treatment group and randomization strata (as per IRT) and the continuous effect of mRSS at baseline. This model will provide the SAR156597 to placebo odds ratio estimate and its 95% and 90% confidence intervals. The p-value will be obtained from the

Wald Chi-square test. Patients with missing value at Week 24, respectively Week 35, will be considered as non-responders. Cumulative distribution function (CDF) graphs will be also presented (percentage of patients according to the relative improvement from baseline in mRSS) at W24 and W35.

Furthermore, the change from baseline to Week 35 will be analyzed using the MMRM model described in [Section 2.4.4.4](#).

Three supplementary definitions for responder rate at Week 24 will be used and analyzed using a logistic regression with the categorical effects of treatment group and randomization strata (as per IRT) and the continuous effect of mRSS at baseline:

- Responder rate defined as the proportion of patients with an improvement from baseline in mRSS of at least 25% at Week 24.
- Responder rate defined as the proportion of patients with an improvement from baseline in mRSS of at least 25% at Week 24 and no intake of rescue medication.
- Overall responder rate defined as the proportion of patients with an improvement from baseline in mRSS of at least 25% and without CRISS event and no intake of rescue medication and alive at W24 are defined as responder.

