8.8.1 Prohibited concomitant medications

- High dose immunosuppressive drugs will be prohibited (eg, cyclophosphamide >1 mg/kg oral/day or >750 mg IV/month; azathioprine >100 mg/day; methotrexate >15 mg/week, mycophenolate mofetil >2 g/day) within 3 months prior to screening and during the course of the trial, a change in dose within 4 weeks prior to randomization (or baseline visit) or expected changes in dose during the course of the study will be prohibited.
- High dose steroids (>10 mg/day prednisone equivalent); or a change in steroid dose within 4 weeks prior to randomization (or baseline visit) or expected changes in dose during the course of the study will be prohibited.
- Treatment with etanercept, cyclosporine A, IVIG, rapamycin, D-penicillamine, tyrosine kinase inhibitors within 4 weeks of screening, antithymocyte globulin within 6 months of screening and during the course of the study will be prohibited.
- Treatment with infliximab, certolizumab, golimumab, abatacept, or adalimumab, totilizumab within 8 weeks of screening, anakinra with 1 week of screening and during the course of the study will be prohibited.
- Treatment with rituximab within 12 months prior to screening and during the course of the study will be prohibited.
- Treatment with any investigational drug for SSc during the course of the study will be prohibited.

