2.1.2 Prior or concomitant medications

All immunosuppressive and investigational drugs taken within 3 months before screening visit, all antibiotics taken within 1 month before screening visit, and all medications taken within 28 days prior to baseline visit and until the end of the study are to be reported in the case report form pages.

All medications will be coded using the World Health Organization-Drug Dictionary (WHO-DD) using the version currently in effect at Sanofi at the time of database lock.

- Prior medications are those the patient used prior (from 3 months before screening visit) to first investigational medicinal product (IMP) intake. Prior medications can be discontinued before first administration or can be ongoing during treatment phase.
- Concomitant medications are any treatments received by the patient concomitantly to the IMP, from randomization to the end of treatment + 84 days. A given medication can be classified both as a prior medication and as a concomitant medication. Concomitant medications do not include medications started during the post-treatment period (as defined in the observation period in [Section 2.1.5](#)).
- Post-treatment medications are those the patient took in the period running from the day after last administration of IMP + 84 days up to the end of the study.

Any technical details related to computation, dates, imputation for missing dates are described in [Section 2.5](#).

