2.4.2 Prior or concomitant medications

The prior and concomitant medications will be presented for the randomized population.

Medications will be summarized by treatment group according to the WHO-DD, considering the first digit of the anatomic category (ATC) class (anatomic category) and the first 3 digits of the ATC class (therapeutic category). All ATC codes corresponding to a medication will be summarized, and patients will be counted once in each ATC category (anatomic or therapeutic) linked to the medication. Therefore patients may be counted several times for the same medication.

The table for prior medications will be sorted by decreasing frequency of ATC followed by all other therapeutic classes based on the overall incidence across treatment groups. In case of equal frequency regarding ATCs (anatomic or therapeutic categories), alphabetical order will be used.

Patients who received background therapy are defined as all patients who took a medication from the anatomic classes of “antineoplastic/immunomodulating agents” and/or “systemic hormonal preparations, excl. sex hormones and insulins” (see [Appendix J](#)) before and at baseline.

The second definition of patients who received background therapy is defined as all patients taken “methotrexate, mycophenolate mofetil, azathioprine, ciclosporin, and cyclophosphamide” (see [Appendix J](#)) before and at baseline.

The tables for concomitant and post-treatment medications will be sorted by decreasing frequency of ATC followed by all other therapeutic classes based on the incidence in the SAR156597 group. In case of equal frequency regarding ATCs (anatomic or therapeutic categories), alphabetical order will be used.

The patients who took a rescue medication during the study are defined according to the deviation “Prohibited use of immunosuppressive therapies as concomitant medications”.

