3 INTERIM ANALYSIS

As there is no major enrollment issue, no futility analysis is planned.

Early analysis:

The primary analysis of efficacy and safety will be performed on the data collected during the 24-week treatment period. The results of this analysis will not be used to change the conduct of the follow-up in any aspect.

The analysis will be conducted in two steps:

- First step: Main efficacy and safety analyses.
- The first analysis will be conducted when all patients have been randomized and have at least all their data up to Week 24 collected and validated, and will consist in the final analysis of the efficacy endpoints up to Week 24. The safety analysis will be performed on all safety data collected and validated at the time of first analysis. The results of the first analysis will not be used to change the conduct of the ongoing study in any aspect. The 24-week data will not be reanalyzed at the end of the study. Individuals who have access to patients' source documents will remain blinded with regards to the treatment arm of individual patients throughout the study. Treatment arm will not be disclosed on Data Surveillance reports.
- Second step: Final analysis.
- The second analysis will be conducted at the end of the study and will consist in the final analysis of Week 35 efficacy endpoints and final safety analysis.

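### Read literally, the second supplementary Week 24 mRSS responder definition lets rescue medication started after Week 24 cancel a Week 24 response

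*SAP*

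**What the plan says.** SAP 2.4.4.4.1 adds three responder rates built on a 25% mRSS improvement, introduced by "Three supplementary definitions for responder rate at Week 24 will be used". The first has no rescue clause. The second requires "improvement from baseline in mRSS of at least 25% at Week 24 and no intake of rescue medication". The third, the overall responder rate, adds further conditions to the 25% improvement and ends "without CRISS event and no intake of rescue medication and alive at W24 are defined as responder".

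Rescue is defined only in SAP 2.4.2: "The patients who took a rescue medication during the study are defined according to the deviation", followed by the name of the deviation category for prohibited immunosuppressants used as concomitant medication. No cut-off date is given. SAP 2.1.2 sets the concomitant period as "from randomization to the end of treatment + 84 days"; medication started later is classed as post-treatment.

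Protocol 8.8.1 prohibits high-dose immunosuppressants "within 3 months prior to screening and during the course of the trial", and Protocol 8.8.2 does not allow low-dose ones to be started while the study runs. The flow chart has concomitant medication recorded at Weeks 24, 30 and 35. Under SAP 3 and 4, Week 24 efficacy is analysed at a first lock four weeks after the last patient's Week 24 visit, and "The 24-week data will not be reanalyzed at the end of the study".

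**The concern.** A Week 24 responder rate should depend on what happened up to Week 24. In the second definition, the time reference belongs to the mRSS improvement; the rescue condition is a patient-level flag taken from a definition that spans the study. A programmer who follows SAP 2.4.2 and 2.4.4.4.1 as written would classify a patient who improved by 25% at Week 24 and started a prohibited immunosuppressant at Week 28 as a Week 24 non-responder, provided the record was in the database at the first lock.

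Two things are at stake. Events after the endpoint can change the endpoint. And because the Week 24 results are fixed at one calendar date, patients with the same clinical course can be classified differently according to when they enrolled. A second programmer who assumed a Week 24 cut-off would obtain a different rate from the same text.

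**Working it through.** The plan gives no figure for these responder rates, so there is none to reproduce. The check is calendar arithmetic, followed by an illustration of size.

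**Calendar**

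1. SAP Table 3 counts the first injection as Day 1, so target day = 7 × week + 1. Week 24: 7 × 24 + 1 = 169. Week 35: 7 × 35 + 1 = 246. Both agree with Table 3.
2. The last dose is at Week 23 (Protocol flow chart): 7 × 23 + 1 = Day 162. The concomitant period ends 84 days later: 162 + 84 = Day 246. For a treatment completer it therefore ends on the Week 35 target day.
3. Days after the Week 24 target that lie inside that period: 246 − 169 = 77. As a share of the 245 days from Day 1 to Day 246: 77/245 = 31%. This is a ceiling.
4. At the first lock the last patient is near Day 169 + 28 = 197, so about 28 of the 77 days have elapsed. The next scheduled medication review is the Week 30 call, on Day 7 × 30 + 1 = 211, so even those 28 days may be only partly recorded.
5. A patient whose Week 24 visit fell at least 77 − 28 = 49 days before the last patient's has all 77 days elapsed at the lock. Steps 4 and 5 assume visits on target days and a lock at exactly four weeks.
6. If the flag is tied to the concomitant period, the window can also be too short. A last dose at Week 4 (Day 29) gives 29 + 84 = Day 113, which is before Week 24. Since 85 + 84 = 169, any last dose before Day 85 leaves a gap in which a drug started before Week 24 counts as post-treatment medication.

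**Size (assumed rates; the documents give none)**

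Responders reclassified per arm = 47 × response rate × share of responders starting rescue after Week 24.

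- Low end: 47 × 0.30 × 0.02 = 0.3.
- Middle: 47 × 0.40 × 0.10 = 1.9; the rate falls from 40% to 0.40 × 0.90 = 36%.
- High end: 47 × 0.50 × 0.15 = 3.5.

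The effect on the treatment difference depends on the split between arms. Take 20/47 versus 12/47 responders, a difference of 8/47 = 17.0 points. If 10% of responders in each arm are reclassified, it becomes (18 − 10.8)/47 = 15.3 points. If 4 active and 1 placebo responders are reclassified, it becomes (16 − 11)/47 = 10.6 points. All these counts are assumptions.

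**The case against.** The strongest reply is that the SAP already points to Week 24. The three definitions are introduced as responder rates at that week. SAP 3 says the primary analysis of efficacy and safety uses data from the 24-week treatment period. No text says that rescue started later counts. These points support a Week 24 reading, but they are general statements. The specific definition in SAP 2.4.2 refers to the study, and nothing in 2.4.4.4.1 narrows it for the second definition. How the deviation category is dated in practice is not stated in the protocol or SAP.

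Several limits on the point stand:

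- A reader might infer that both rescue-based definitions are affected. In the third, the closing reference to Week 24 is the only date in the bullet. It must govern the improvement clause, so it probably governs the rescue and CRISS-event clauses as well.
- A reader might infer that the flag runs to Week 35 for everyone. It cannot: Week 24 results are fixed at the first lock and not rerun, and the 84-day period reaches Day 246 only for patients who complete treatment.
- A reader might infer that the loss falls mainly on active-arm responders who relapse after stopping drug. The documents contain no relapse or rescue rates, so this is conjecture, and the 10.6-point case above rests wholly on its assumed split.
- These are supplementary definitions of an exploratory endpoint, with descriptive p-values (SAP 2.4.4.3). The first supplementary definition and the 20%, 40% and 60% rates have no rescue clause and are reported alongside.

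**Conclusion.** The point holds for the second definition on a literal reading: its rescue condition has no Week 24 cut-off, and the look-back at the first lock would range from about 28 days after Week 24 for the last patient to 77 for early enrollees. The third definition needs clarification rather than correction. The number of patients affected cannot be estimated from the documents; 0.3 to 3.5 responders per arm is a range under assumed rates. With 47 per arm, the upper part of that range would visibly move a responder rate. The consequence is confined to supplementary exploratory results, and neither the primary MMRM nor its power is affected. It is worth correcting because a stated rule, followed as written, makes a Week 24 endpoint depend on later events and on enrolment date.

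**What to change.** In SAP 2.4.2 and 2.4.4.4.1, state that for the Week 24 responder definitions rescue medication counts only if taken from randomization up to and including the date of the Week 24 mRSS used in the analysis, whether or not IMP was stopped earlier. Apply the same window to the CRISS-event clause of the third definition. Starting at randomization covers patients randomized but never treated, who belong to the ITT population. Removing the link to the end of treatment closes the gap for early discontinuers.

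The survival condition in the third definition is already dated and needs no change. No fallback date is needed if patients with a missing Week 24 mRSS are counted as non-responders. SAP 2.4.4.4.1 says so for the 20%, 40% and 60% rates and should repeat it for the supplementary definitions.

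The cost is a sentence or two in the SAP and a date condition in the program. Medication dates are already collected. The change should be made before unblinding for the first analysis.
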